Further details will be described in the site manuals (e.g. Laboratory Manual, Site Operations Manual, Pharmacy Manual).

Note: In case of early discontinuation, the subject should be encouraged to perform end-of-treatment assessments as detailed for the MAD Week 25 visit (excluding IMP administration). In addition, subjects will be encouraged to have the second muscle biopsy taken if the subject had at least 6 weeks of treatment during the MAD part of the trial and discontinued prior to having the Week 13 biopsy obtained. If subjects agree, they will also have an EoT FU visit 3 months after their last IMP administration.

5) MAD EXTENSION PART

MAD EXTENSION PART															
Trial Period	Multiple Dose Treatment Period ^{a)}													EoT/ED	EoT FU
Time Point: Week (W)	MAD W13	MAD W14	MAD W15	MAD W16	MAD W17	MAD W18	MAD W19	MAD W20	MAD W21	MAD W22	MAD W23	MAD W24	MAD W25	MAD Last dose + 3 months ^{b)}	
Time Window	±3d	±3d	±3d	±3d	±3d	±3d	±3d	±3d	±3d	±3d	±3d	±3d	±3d	±3d	
Administrative															
Concomitant medications	✓	✓	✓	✓	✓	✓	✓	✓	✓	✓	✓	✓	✓	✓	
IMP administration (IV) ^{c)}	✓	✓	✓	✓	✓	✓	✓	✓	✓	✓	✓	✓	✓ ^{d)}		
Safety Assessments															
Physical examination ^{e)}	✓						✓						✓ ^{f)}	✓	
Triplicate 12-lead ECG	✓						✓						✓		
Vital signs (pulse rate, BP, RR, temperature, pulse oximetry) ^{f)}	✓	✓	✓	✓	✓	✓	✓	✓	✓	✓	✓	✓	✓	✓	
Platelet count ^{f) g)}	✓		✓		✓		✓		✓		✓		✓	✓	
Clinical laboratory tests ^{f) h)}	✓		✓		✓		✓		✓		✓		✓	✓	
Cardiac troponin ^{f) i)}	✓				✓				✓				✓	✓	
Complement assessments ^{f) i)}	✓				✓				✓				✓	✓	
Coagulation assessments ^{f) j)}	✓		✓		✓		✓		✓		✓		✓	✓	
Erythrocyte sedimentation rate ^{f) j)}	✓		✓		✓		✓		✓		✓		✓	✓	
Urinalysis (dipstick) ^{f)}	✓				✓				✓				✓		
Urine pregnancy test ^{f) k)}	✓				✓				✓				✓		
Collect AEs/SAEs	✓	✓	✓	✓	✓	✓	✓	✓	✓	✓	✓	✓	✓	✓	
PK Assessments															
Blood sample for PK	✓ ^{l)}												✓ ^{l)}		
Blood sample for anti-drug antibodies ^{f)}	✓						✓						✓		

MAD EXTENSION PART														
Trial Period	Multiple Dose Treatment Period ^{a)}												EoT/ED	EoT FU
Time Point: Week (W)	MAD W13	MAD W14	MAD W15	MAD W16	MAD W17	MAD W18	MAD W19	MAD W20	MAD W21	MAD W22	MAD W23	MAD W24	MAD W25	MAD Last dose + 3 months ^{b)}
Time Window	±3d	±3d	±3d	±3d	±3d	±3d	±3d	±3d	±3d	±3d	±3d	±3d	±3d	±3d
Blood sample for metabolic profiling	✓ ^{l)}													
PD/Exploratory Efficacy Assessments														
Blood sample for biomarkers (optional) ^{f)}	✓						✓						✓	

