PROMIS and GAS questionnaires ^{f)}	✓						✓						✓	
CGI-I and PGI-C questionnaires ^{f)}	✓												✓	
EAT-10 Dysphagia questionnaire ^{f)}	✓												✓	
Respiratory function ^{f) m)}	✓						✓						✓	
MyoGrip ^{f) m)}	✓						✓						✓	
MFM32 ^{f) m)}	✓						✓						✓	
Muscle biopsy ^{m)}	✓ ⁿ⁾												(✓) ^{o)}	

AE: adverse event; BP: blood pressure; CGI-I: Clinical Global Impression of Improvement; EAT-10: Eating Assessment Tool; ECG: electrocardiogram; ED: early discontinuation; EoT: End of Treatment; FU: follow-up; GAS: Goal Attainment Scaling; IMP: investigational medicinal product; IPF; immature platelet fraction; IV: intravenous; MAD: multiple ascending dose; MFM: Motor Function Measure; PD: pharmacodynamics; PGI-C: Patient Global Impression of Change; PK: pharmacokinetics; PROMIS: Patient Reported Outcomes Measurement Information System; RR: respiratory rate; SAE: serious adverse event.

- Where possible, the visits in the MAD extension part will take place on the same day of the week as MAD Week 1 Day 1. A window of ±3 days is allowed, with a minimum of 4 days between 2 subsequent infusions. Assessments of a single visit can be split over 2 consecutive days, if required.
- If a subject is NOT on treatment after the trial, the subject will return to the clinic 3 months after the last IMP administration, to follow-up on the subject's status including abnormal laboratory test results, AEs, and concomitant medications.
- Slow infusion over 1 hour; subjects will be monitored on site by qualified site personnel for a minimum of 1 hour after the infusion for safety.
- The subject may continue to receive IMP weekly with clinic visits every 2 weeks with assessments as defined in the Trial Schedule for Follow-up post MAD Week 25.
- A symptom-directed physical examination (and measurement of body weight at MAD Week 13) will be performed. A neurologic assessment is also to be performed at the EoT/ED and EoT FU visit.
- To be performed pre-dose.

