- g) Platelet counts will be assessed by the local as well as the central laboratory. Platelet counts as determined by the local laboratory need to be within normal ranges before IMP administration. If a decreased platelet count is detected (value < LLN), a retest should be performed immediately in the local laboratory. If this retest confirms that the platelet count value is below LLN, the subject may NOT be dosed. For details see Section 7.11.2. If platelet clumping is observed in a local sample, the test should be repeated locally before IMP administration. In addition, smear may be performed locally at the investigator's discretion. If thrombocytopenia is reported, and if an IPF test is available at the local laboratory, IPF test results should be obtained in addition to the platelet count. The IPF is the ratio of immature platelets to the total number of platelets, indicating the percentage of young, so-called 'reticulated' platelets.
- h) All parameters that are not described in a separate assessment in this Trial Schedule are to be performed by the central laboratory, as specified in Section 6.2.2.2.
 - i) Will be assessed by the central laboratory.
 - j) Will be assessed by the local laboratory, only.
 - k) Only applicable for female subjects of child-bearing potential.
- l) Blood samples for PK and metabolic profiling at MAD Week 13 must be collected 167 hours after the end of infusion from MAD Week 12 Day 1 visit and before the infusion of MAD Week 13 visit. Blood sample for PK at MAD Week 25 must be collected 167 hours after the end of infusion from MAD Week 24 Day 1 visit and before the infusion of MAD Week 25 visit, where applicable.
- m) Assessments should be performed in the order they are listed after all the questionnaires.
- n) The muscle biopsy should be obtained after all muscle assessments have been performed. Platelet counts as determined by the local laboratory need to be within normal ranges before performing the muscle biopsy. In case general anesthesia is used for an open biopsy (see Section 6.2.6), there should be at least 24 hours between the muscle biopsy and the IMP administration. Consequently, platelet counts will need to be verified again before IMP administration (local assessment) only if previous platelet count is more than 3 days old.
- o) See note about early discontinuation assessments below.

Further details will be described in the site manuals (e.g. Laboratory Manual, Site Operations Manual, Pharmacy Manual).

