Note: In case of early discontinuation, the subject should be encouraged to perform end-of-treatment assessments as detailed for the MAD Week 25 visit (excluding IMP administration). In addition, subjects will be encouraged to have the second muscle biopsy taken if the subject had at least 6 weeks of treatment during the MAD part of the trial and discontinued prior to having the Week 13 biopsy obtained. If subjects agree, they will also have an EoT FU visit 3 months after their last IMP administration.

6) FOLLOW-UP POST MAD WEEK 25

All subjects will remain on treatment with weekly IMP administrations and routine safety assessments performed as noted in the table below until the last MAD3 subject has completed the MAD Week 25 visit. All assessments are to be performed prior to IMP administration.

12-week Follow-up Cycle Repeated After Week 25						
Time Point	Weeks 1, 3, 5, 7, 9, and 11	Weeks 2, 6, and 10	Weeks 4 and 8	Week 12	EoT	EoT FU Visit
Time Window ^{a)}	±3d	±3d	±3d	±3d	±7d	3 months after last IMP administration
Administrative						
Concomitant medications	✓	✓	✓	✓	✓	✓
IMP administration (IV) ^{b)}	✓	✓	✓	✓		
Safety Assessments						
Physical examination ^{c)}				✓	✓	✓
Triplicate 12-lead ECG				✓	✓	
Vital signs (pulse rate, BP, RR, temperature, pulse oximetry) ^{d)}	✓	✓	✓	✓	✓	✓
Platelet count ^{d) e)}		✓	✓	✓	✓	✓
Clinical laboratory tests ^{d) f)}		✓	✓	✓	✓	✓
Cardiac troponin ^{d) g)}			✓	✓	✓	✓
Complement assessments ^{d) g)}			✓	✓	✓	✓
Coagulation assessments ^{d) h)}		✓	✓	✓	✓	✓
Erythrocyte sedimentation rate ^{d) h)}		✓	✓	✓	✓	✓
Urinalysis (dipstick) ^{d)}		✓	✓	✓	✓	
Urine pregnancy test ^{d) i)}		✓	✓	✓	✓	
Collect AEs/SAEs	✓	✓	✓	✓	✓	✓
PK Assessments						
Blood sample for anti-drug antibodies ^{d)}				✓	✓	
PD/Exploratory Efficacy Assessments						
Blood sample for biomarkers (optional) ^{d)}				✓	✓	

12-week Follow-up Cycle Repeated After Week 25						
Time Point	Weeks 1, 3, 5, 7, 9, and 11	Weeks 2, 6, and 10	Weeks 4 and 8	Week 12	EoT	EoT FU Visit
Time Window ^{a)}	±3d	±3d	±3d	±3d	±7d	3 months after last IMP administration
PROMIS and GAS questionnaires ^{d)}				✓	✓	
CGI-I and PGI-C questionnaires ^{d)}					✓	
EAT-10 Dysphagia questionnaire ^{d)}				✓	✓	
Respiratory function ^{d),j)}				✓	✓	
MyoGrip ^{d),j)}				✓	✓	
MFM32 ^{d),j)}				✓	✓	
Muscle biopsy ^{d),j)}						

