6.1.3.4 MAD Extension Part

After completion of the MAD part, subjects will continue on the IMP dose level of their assigned MAD cohort for an additional 12 weeks with weekly IV administrations (MAD Weeks 13-24) (unless the IDMC advises otherwise).

End-of-treatment assessments will be performed after 24 weeks of MAD treatment have been completed, i.e. at the Week 25 visit.

After Week 24, all subjects will remain on treatment with weekly IMP administrations and assessments every 2 weeks until the last MAD3 subject has completed the MAD Week 25 visit. Data collected during this period will be listed and tabulated in the clinical trial report but will not be included in the statistical modeling.

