6.2.2.2 Clinical Laboratory Tests

Clinical laboratory parameters should be monitored at the time points specified in the [TRIAL SCHEDULES](#).

In addition to testing of all parameters (except coagulation and erythrocyte sedimentation rate [ESR]) at the central laboratory, platelet counts will also be assessed locally prior to IMP administration and muscle biopsy. Platelet counts as determined by the local laboratory need to be within normal laboratory references ranges before IMP administration (at the time points specified in the [TRIAL SCHEDULES](#)), or before performing a muscle biopsy. The samples for platelet count verification cannot be older than 3 days. Any discrepancy between the results of the local and central laboratory should be discussed with the medical monitor before any further IMP administration. The coagulation panel and ESR will only be tested locally; they will NOT be repeated at the central laboratory. If thrombocytopenia is reported during the trial after the first IMP administration, and if an immature platelet fraction (IPF) test is available at the local laboratory, IPF test results should be obtained in addition to the platelet count. The IPF is the ratio of immature platelets to the total number of platelets, indicating the percentage of young, so-called 'reticulated' platelets.

All clinical laboratory assays will be performed according to the local or central laboratory's normal procedures. Normal reference ranges which are age- and gender-specific (as applicable) are supplied by the respective laboratories and used to assess the clinical laboratory data for clinical significance and out-of-range pathological changes. The investigator should assess out-of-range clinical laboratory values for clinical significance, indicating if the value(s) is/are not clinically significant or clinically significant.

The following clinical laboratory assessments will be performed:

Biochemistry:

General	Liver function tests	Kidney function tests	Other
- sodium	- AST	- BUN	Cardiac Safety - creatine kinase myocardial band (CK-MB)
- potassium	- ALT	- creatinine	- cardiac troponin
- chloride	- ALP	- cystatin C	
- calcium	- GGT	- eGFR ^{a)}	
- magnesium	- bilirubin: direct, indirect, and total		
- phosphorus	- albumin		Muscle injury
- bicarbonate	- total protein		- creatine kinase
- glucose	- bile acids		
- CRP			
- IgG and IgM			
- LDH			

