7.11.2 Individual Treatment Interruptions and Dose Adjustments

As thrombocytopenia is a known side effect of ASOs, it is important to always check that the subject has a normal platelet count before dosing. If a decreased platelet count is detected (i.e. value $<$ lower limit of normal [LLN]), a retest should be performed immediately in the local laboratory. If the retest confirms a platelet count value $<$ LLN, the subject may NOT be dosed.

Treatment interruptions will be considered in the event of any suspicion of vasculitis or in the event of any of the following situations that may occur, considered related to IMP:

- Platelet count is between 75,000 and 150,000/ μ L; in that case the subject can be dosed as soon as the platelet count has returned to a value $>$ LLN and dosing can resume at the same dose.
- Platelet count is $<$ 75,000/ μ L; in that case the subject can be dosed as soon as the platelet has returned to a value $>$ LLN, however dosing should be resumed at 50% of the previous dose.
- Platelet count is $<$ LLN and a previous dose interruption had taken place because of decreased platelet values; in this case, the medical monitor should be contacted to discuss possible additional treatment interruptions and/or dose adjustments.

Furthermore, treatment interruptions and/or dose adjustments for an individual subject should be considered in the event of any of the following events:

- Elevation of AST and/or ALT $>$ 3 \times ULN
- Elevation of bilirubin $>$ 2 \times ULN
- Elevation of ALP $>$ 1.5 \times ULN
- Elevation of ALT and/or AST in temporal association with nausea, vomiting, anorexia, abdominal pain, or fatigue
- Clinically significant deteriorating kidney function during treatment
- Any other clinically significant deterioration during treatment considered related to IMP.

In these instances, the medical monitor should be contacted to discuss potential treatment interruptions and/or dose adjustments.

In case a treatment interruption is needed for any safety reason for more than 4 consecutive weeks, or if there is a second treatment interruption on the initial or reduced dose level, the site should always contact the medical monitor to determine the best strategy for the subject, considering the individual risk-benefit ratio.

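### Protocol 7.11.2 says a normal platelet count is always checked before dosing, but the schedules have no count at 6 of every 12 weekly doses from Week 13, and nothing beyond that schedule is required once dosing resumes after a platelet hold

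*Protocol*

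**What the plan says.** Protocol 7.11.2 opens by stating that "it is important to always check that the subject has a normal platelet count before dosing". A value below the lower limit of normal (LLN) is retested at once, and if confirmed the subject is not dosed. Section 3.2.3 also requires a normal local count before IMP and names no time points.

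Other places tie the check to the schedule. Section 6.2.2.2 says that local counts "need to be within normal laboratory references ranges before IMP administration (at the time points specified in the" Trial Schedules, and adds: "The samples for platelet count verification cannot be older than 3 days". Sections 1.5 and 7.2 carry the same restriction to scheduled time points.

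Dosing is weekly throughout MAD Weeks 1 to 24 (Protocol 6.1.3.3 and 6.1.3.4). In the MAD part the platelet row is ticked at every dosing visit. In the MAD extension it is ticked at Weeks 13, 15, 17, 19, 21, 23 and 25 only. After Week 25 weekly dosing goes on, and the platelet footnote names Weeks 2, 4, 6, 8, 10 and 12 of each 12-week cycle.

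After a platelet hold, 7.11.2 lets dosing resume once the count is back above LLN: at the same dose, or at 50% if the count had been under 75,000/µL. It says nothing about counts before the doses that follow.

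SAP 6.2.11 leaves post-baseline repeat and unscheduled laboratory values out of the tables and keeps them in listings. SAP 6.14.2 defines the laboratory shift table as baseline to the worst recorded result in each trial period, and reports local platelet counts in the laboratory tables.

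**The concern.** The hold can act only on a count that has been taken. A site that follows the schedule at Week 14 doses without a count; a site that follows 7.11.2 does not. The protocol does not say which governs.

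The gap matters most after a hold. Take a subject under 75,000/µL at Week 15 who recovers and restarts at 50% at Week 17. The next reduced dose, at Week 18, has no scheduled count, although this is when a renewed fall most needs to be seen.

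Thrombocytopenia is an adverse event of special interest (7.2), and a marked platelet reduction in two animals was the most noteworthy finding of the 13-week monkey study (3.2.5). Counting goes from weekly to two-weekly at Week 13 while dosing stays weekly. The protocol gives no reason for the change and does not make it depend on a subject's platelet history.

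**Working it through.** **1. Reproduce the plan's own figure.** Table 4 (6.2.7) gives 31 local platelet samples of 1.0 mL per subject up to MAD Week 25. The ticks in the Trial Schedules give:

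| Period | Visits with a platelet count | Number |
|---|---|---|
| Screening | one | 1 |
| SAD baseline | one | 1 |
| SAD follow-up | Days 8, 15, 29, 43, 57, 71, 85, 99, 113 | 9 |
| MAD | Days 1, 4, 8; Weeks 3 to 12 | 13 |
| MAD extension | Weeks 13, 15, 17, 19, 21, 23, 25 | 7 |
| Total | | 31 |

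1 + 1 + 9 + 13 + 7 = 31, which matches. As a cross-check, erythrocyte sedimentation rate has the same visits without screening: 31 − 1 = 30, also as in Table 4. The odd-week pattern is therefore the plan and not a fault in reading the table.

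**2. Set doses against counts.**

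- SAD: 1 dose, 1 with a scheduled pre-dose count.
- MAD Weeks 1 to 12: 12 doses, 12 with a count.
- Extension Weeks 13 to 24: 12 doses, 6 with a count (13, 15, 17, 19, 21, 23) and 6 without (14, 16, 18, 20, 22, 24).
- Up to Week 24: 1 + 12 + 12 = 25 doses, 6 without a count; 6/25 = 24%.
- Each 12-week cycle after Week 25: 12 doses, 6 without a count (Weeks 1, 3, 5, 7, 9, 11).

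**3. Can the previous week's count serve?** Extension counts are taken pre-dose, and infusions are given "with a minimum of 4 days between 2 subsequent infusions". At an even-week dose the last scheduled count is therefore at least 4 days old, nominally 7, and up to 7 + 3 + 3 = 13 days with the ±3-day windows. The minimum of 4 days exceeds the 3-day sample limit in 6.2.2.2, so an odd-week count cannot meet the 7.11.2 statement at the next dose by being carried forward.

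**4. Cost of a count before every dose.** 31 + 6 = 37 samples; 31.0 + 6 × 1.0 = 37.0 mL local platelet volume; Table 4 total 902.5 + 6.0 = 908.5 mL (6/902.5 = 0.7%). After Week 25 it is 6 × 1.0 = 6 mL per cycle.

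**The case against.** The strongest answer is that the schedule governs and two-weekly counting is deliberate. Sections 1.5, 6.2.2.2 and 7.2 all point to the scheduled time points. In the SAD and MAD schedules the footnote on the IMP row itself asks for a normal local count; in the extension and post-Week 25 schedules the IMP-row footnote drops that sentence, and it remains only on the platelet row. Table 4 is budgeted to match. This stands. It makes the schedule the likelier intention, but it does not remove the unlimited wording from 7.11.2, which holds the operative rule, or from 3.2.3.

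A reader might therefore infer too much in three ways:

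- **That the protocol mandates six counts the schedule forgot.** The wording in 7.11.2 stresses importance and is not a strict requirement. The extension footnote ("Platelet counts as determined by the local laboratory need to be within normal ranges before IMP administration") sits on the platelet row and does not clearly reach unticked visits. The 3-day limit follows a sentence restricted to scheduled time points, so it sets the age of a sample used at a required check and does not itself require one at Week 14.
- **That nothing protects a subject after a hold.** A recovered count above LLN is needed before restart. Section 4.5 calls for discussion with the medical monitor on a temporary discontinuation, 6.2.2 allows abnormal tests to be repeated, 7.2 requires examination and retest on a fall plus bleeding queries, and 7.10 provides follow-up of related events. These leave later counts to discretion; none fixes one before Week 18.
- **That two-weekly counting is shown to be unsafe.** It is not. The documents give no rate of platelet falls. The monkey finding was at 30 mg/kg, against a no-effect level of 10 mg/kg and a top human dose of up to 9 mg/kg, and 3.2.5 states that counts recover.

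Nor would a low unscheduled count be lost: it stays in the laboratory and abnormal-value listings, and a fall reported as an event of special interest appears in that table. The SAP point is narrower: a worst-result shift table that omits retests may not show the worst result.

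**Conclusion.** The point holds as an internal contradiction in a safety rule. Sections 7.11.2 and 3.2.3 describe a check before dosing without limit; the schedules provide none at 6 of 12 extension doses (6 of 25 doses up to Week 24) or at 6 of 12 doses in each later cycle. Separately, after a platelet hold no count is required beyond the two-weekly schedule once the first dose has been resumed.

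These counts rest on the schedule ticks, confirmed by Table 4, and on a subject receiving every planned dose. They describe scheduled counts only: sites may have taken more, since 6.1 allows unscheduled samples. No harm is shown and no expected number of subjects is claimed.

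The trial was stopped early (SAP 8), so for the data in hand this is a reporting matter. The SAP revision table says that a summary of doses was added because of many interruptions, but gives no reasons for them, so it is not evidence of platelet holds.

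**What to change.** Choose one of two and make all the sections agree.

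1. **Count before every infusion.** Add a local count, no older than 3 days, at each unticked dosing visit in the extension and post-Week 25 schedules. Cost: 37 instead of 31 samples and 908.5 instead of 902.5 mL up to Week 24, then 6 mL per cycle. No visits are added, because infusions are already weekly and monitored on site. The drawback is waiting for the local result before each infusion.
2. **Keep two-weekly counts.** Limit 7.11.2 and 3.2.3 to the scheduled time points. After any platelet hold, require a local count before each dose until a stated number of consecutive normal counts, the number to be set by the sponsor. Cost: wording, plus a few samples in held subjects.

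In SAP 6.2.11, except platelets: include unscheduled and retest counts in the shift table to the worst recorded result. Because the trial has stopped, list in the clinical study report the doses given with no local count in the preceding 3 days. That is one listing from existing dosing and local laboratory dates.

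A minor wording note: the first interruption band in 7.11.2 ends at 150,000/µL while hold and restart use the local LLN. Ending the band at LLN would remove the mismatch.

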8. DATA MANAGEMENT

8.1 Data Collection

The investigators' authorized site personnel must enter the information from the source data (see Section 10.2.3.2), as required by the protocol, in the eCRF (see Section 10.2.3.1). A monitor will visit each site in accordance with the monitoring plan and review the eCRF data against the source data for completeness and accuracy. Discrepancies between source data and data entered in the eCRF will be addressed by qualified site personnel. When a data discrepancy warrants correction, the correction will be made by authorized site personnel. Data collection procedures will be discussed with the site personnel at the site initiation visit and/or at the investigator's meeting.

